#### **17.1.1. SEVERITY GRADING FOR AEs**

Severity will be classified as mild, moderate, severe, potentially life-threatening and fatal (increasing severity) by using the FDA Grading for AEs. Should a participant experience multiple events within a SOC or PT, only the participants' worst FDA grade will be counted for that SOC or PT.

#### **17.1.2. RELATIONSHIP TO STUDY INTERVENTION/NON-STUDY INTERVENTION/PROCEDURE**

Relationship to study intervention/procedure, as indicated by the Investigator, will be classified as not related, related.

#### **17.1.3. ADVERSE EVENTS WITH AN OUTCOME OF DEATH**

AEs with an outcome of death are those events which are recorded as "Fatal" on the AE page of the eCRF. A summary of AEs with an outcome of death by SOC and PT will be prepared.

A listing of all AEs with an outcome of death will be provided.

#### **17.1.4. SERIOUS ADVERSE EVENTS**

SAEs are those events recorded as "Yes" for the question "Serious Event?" on the AE page of the eCRF.

SAEs post the first study intervention, including exposure adjusted rates, will be summarized by SOC and PT by cohort. Specific SAEs will be counted once for each participant for calculating percentages. If the same SAE occurs multiple times within a particular participant, the highest severity observed will be reported. A summary of related SAEs post the first study intervention, including exposure adjusted rates, will be presented by SOC and PT by cohort as well.

A listing of all SAEs will be provided. For SAEs with partial dates, if the known part of the date indicates that SAE stopped before the first study intervention, it will be considered as SAE prior to the first study intervention.

Otherwise, it will be considered as SAE post the first study intervention.

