## 6.2. BASELINE

Unless otherwise specified, baseline is defined as the last non-missing measurement taken prior to the first dose of study intervention (including unscheduled assessments). In the case where the last non-missing measurement and the date and time of the first dose of study intervention coincide, that measurement will be considered pre-baseline, but adverse events (AEs) and medications commencing on the date of the first dose of study intervention will be considered post-baseline.

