### 7.2. MISSING DATA

Missing safety data will not be imputed. Partial or completely missing medication dates will be handled as described in [APPENDIX 1](#). Partial or completely missing medical history/concomitant illness dates will be handled similarly.

Missing immunogenicity data will be handled as described in [Section 16.1.5](#) of this analysis plan.

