## 12. CONCOMITANT ILLNESSES

Concomitant conditions/illnesses are defined as any medical conditions/illnesses that started before the first dose of study intervention AND were ongoing at the time of the first dose of study intervention or ended on the first dose of study intervention.

Concomitant conditions/illnesses will be coded using the MedDRA, version 23.0 or higher, and will be summarized by SOC and PT overall and by cohort based on the SAF analysis set. A participant having more than one medical condition/illness within the same SOC or PT will be counted only once for that SOC or PT.

All concomitant conditions/illnesses will be listed.

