## 17. SAFETY ENDPOINTS

All safety summaries will be presented by cohort based on the SAF analysis set. There will be no statistical comparisons between the cohorts for safety data.

The secondary safety endpoints are:

- Reactogenicity: Incidence of local and systemic solicited AEs for 7 days after each dose of AZD1222 by eDiary.
- Incidence of unsolicited AEs for 28 days post dose after each vaccination.
- Incidence of Serious adverse events (SAEs), Medically attended adverse events (MAAEs) and AEs of special interest (AESIs) from Day 1 post treatment to last study visit.
- Absolute and change from baseline for safety laboratory measures

There are also other safety endpoints such as vital signs.

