### 17.1. ADVERSE EVENTS

All AEs are considered to be unsolicited AEs (collected by 'open question' at study visits) unless categorized as solicited AEs recorded in an eDiary (see [Section 17.2](#)).

Non-serious AEs will be recorded for 28 days post each dose of study intervention. SAEs will be recorded from the time of signature of the informed consent form through the last participant contact. MAAEs and AESIs will be recorded from Day 1 through the last participant contact.

AEs will be coded using the MedDRA dictionary, version 23.0 or higher.

Overall summaries of number and percentage of participants, and number of events with following AE categories will be provided by cohort based on the SAF:

- All AEs

- All SAEs
- Related AEs by severity
- Related SAEs
- AEs leading to discontinuation from study intervention
- Related AEs leading to discontinuation from study intervention
- AEs leading to study discontinuation
- Related AEs leading to study discontinuation
- COVID-19 related AEs
- MAAEs
- AEs with outcome of death
- AESIs
- Related AESIs

Should a participant experience multiple events within a category, the participant will be counted only once for that category.

An overall summary of number and percentage of participants, and number of events within each of the categories described above will be provided for the period from 1-28 days post any dose by cohort based on the SAF.

Adverse events post the first study intervention occurring within 28 days of each dose will be summarized by SOC and PT by cohort, including exposure adjusted rates. Specific AEs will be counted once for each participant for calculating percentages. Exposure adjusted rate is calculated as number of participants with AEs in categories above/total patient-year exposure to investigational study intervention. Patient years is determined by summing the total number of follow-up days of each participant, and then dividing by 365.25. The exposure period is calculated from time of first intervention to end of study.

Summary of AEs occurring within 28 days post each intervention will be broken down further by post each dose, maximum severity and events related to study intervention. If the same AE occurs multiple times within a particular participant, the highest severity observed will be reported.

Non-serious AEs, including exposure adjusted rates, will be summarized by PT. AEs within 28 days of each study intervention will also be summarized by PT.

All AEs will be listed.

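### The partial-date rule for SAEs tests only the stop date, so a partially dated SAE with known pre-dose onset that is not shown to have ended before dose 1 is classed as post-dose

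*SAP*

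**What the plan says.** Section 17.1.4 defines an analysis restricted to the post-dose period: "SAEs post the first study intervention, including exposure adjusted rates, will be summarized by SOC and PT by cohort". A matching table is planned for related SAEs. For SAEs with partial dates, the section then gives the only rule in the SAP for deciding which side of dose 1 they belong to: "if the known part of the date indicates that SAE stopped before the first study intervention, it will be considered as SAE prior". The default follows: "Otherwise, it will be considered as SAE post the first study intervention".

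Four other places bear on this:

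- Section 17.1, on collection: "SAEs will be recorded from the time of signature of the informed consent form through the last participant contact". Events before dose 1 are therefore in the database by design.
- Section 17, on the SAE endpoint: incidence is counted "from Day 1 post treatment to last study visit".
- Section 6.2, on placing AEs relative to baseline: "adverse events (AEs) and medications commencing on the date of the first dose of study intervention will be considered post-baseline". The criterion is when the event commences.
- Section 12, on concomitant illnesses: these are conditions that "started before the first dose of study intervention AND were ongoing at the time of the first dose of study intervention" (or ended on that date).

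The addendum leaves the rule unchanged. It reduces the AE outputs to an overall summary, an unsolicited AE summary by system organ class and preferred term, a solicited AE summary and the associated listings.

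**The concern.** Whether an adverse event follows vaccination depends on when it began. The rule in Section 17.1.4 asks instead when it ended. If the recorded month or year of onset already shows that the SAE began before dose 1, the rule discards that information and labels the event post-dose unless it is also known to have resolved before dose 1.

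At stake is the meaning of a secondary safety endpoint, SAE incidence after treatment. Events that vaccination cannot have preceded would enter the numerator. In the exposure-adjusted rates of the main SAP the denominator starts at the first dose, so numerator and denominator would also cover different periods.

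**Working it through.** The SAP gives no figure to reproduce. The check is a comparison of two rules, followed by a simple scale calculation.

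**Step 1. Decision table for partially dated SAEs.** The written rule is set against an onset-based rule that keeps the same conservative default.

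| Known part of start date | Known part of stop date | Written rule | Onset-based rule |
|---|---|---|---|
| Before dose 1 | Before dose 1 | Prior | Prior |
| Before dose 1 | On or after dose 1, ongoing, missing or indeterminate | **Post** | **Prior** |
| On or after dose 1 | Any possible value | Post | Post |
| Indeterminate | Before dose 1 | Prior | Prior |
| Indeterminate | Not shown to be before dose 1 | Post | Post |

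The rules differ only in the second row.

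**Step 2. Worked case (dates assumed).** Dose 1 is on 15 March. An SAE has its start recorded as February with the day missing, and it ended in April or is ongoing. Every day in February precedes 15 March, so onset before dose 1 is certain. The stop is not before dose 1, so the test for prior fails and the default assigns the event to the post-dose period.

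**Step 3. Consistency with the rest of the SAP.** Section 6.2 places AEs by commencement, so the event in Step 2 would be pre-dose. Section 12 treats a condition with the same time course as a concomitant illness. Appendix 1 does use stop dates to separate prior from concomitant medication, but there the question is overlap with treatment, and the algorithm also examines the known start components. The SAE rule has only the stop test.

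**Step 4. Scale.** If the misplaced event is the participant's only post-dose SAE, the percentage of participants with an SAE moves by 1/n. Section 7.1 plans about 60 per cohort, and five immunocompromised cohorts give 5 × 60 = 300.

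- One cohort as planned: 1/60 = 1.7 points.
- Pooled immunocompromised cohorts as planned: 1/300 = 0.3 points.
- The addendum says that the final sample is much smaller than planned but gives no number. Assuming 10 participants, 1/10 = 10.0 points.

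These are shifts per affected participant. They do not estimate how many participants are affected.

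**The case against.** **The default is conservative.** Sending doubtful SAEs to the post-dose period can overcount but does not hide events; all SAEs are listed, and the investigator's relatedness assessment is recorded separately. This stands for truly indeterminate onset, and the fix keeps it. It does not justify ignoring date components that settle the onset.

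**The linked tables are cancelled.** The restriction to post-dose SAEs is attached in Section 17.1.4 to the tables by system organ class and preferred term, which the addendum drops. The overall summary in Section 17.1 lists rows for all SAEs and related SAEs without stating that restriction, and no text says that the partial-date rule drives those rows. This largely stands. A reader might infer that the error certainly reaches the final report. The SAP supports only a conditional statement: it does so if a retained output counts post-dose SAEs, as the overall summary would if it serves the endpoint in Section 17.

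**Complete onset dates.** A reader might infer that an SAE with a complete pre-dose onset and only a partial stop date is also misclassified. That depends on one reading. Section 6.1 gives such an event a negative Study Day and Section 6.2 places AEs by onset, so the rule can be read as a fallback for events whose timing a complete onset does not settle.

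**Other AEs.** A reader might also infer that non-serious AEs, AESIs and MAAEs with partial onset dates drop out of the 28-day table. The documents do not say so. Section 6.1 describes how Study Day appears in listings. Section 7.2 says "Missing safety data will not be imputed", which is not a rule to exclude. Section 17.1 already limits recording of non-serious AEs to the 28 days after each dose. At most, detail is lacking.

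**Conclusion.** The point holds in a narrow form. Read as written, Section 17.1.4 misclassifies one kind of partially dated SAE: onset known to be before dose 1, and stop not shown to be before dose 1. It would be too broad to say that SAEs beginning before the first dose are generally counted as post-dose, because the rule covers only partial dates and correctly classes those known to have ended before dose 1.

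The number of affected events is not given and is probably small, possibly zero. The per-participant shifts rest on planned or assumed group sizes. Nor does the SAP support a claim that such events are more likely in the immunocompromised cohorts. After the addendum the practical effect is limited to retained outputs that count post-dose SAEs. The correction is still worth making, because the rule conflicts with the SAP's own onset criterion and endpoint definition and is easily repaired.

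**What to change.** Replace the rule in Section 17.1.4 with wording to this effect: a partially dated SAE is prior if the known components of its start date show onset before the first dose, or if the known components of its stop date show that it ended before the first dose; otherwise it is post. The conservative default for indeterminate onset is kept.

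It would also help to state in the addendum whether the SAE rows of the retained overall summary count only post-dose events, and that this rule applies to them if so.

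The cost is one sentence of SAP text (a second for the addendum) and a small change to one derivation. No new data are needed. A check of the SAE listing for partial dates would show at once whether any event is affected.

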### **17.1.5. AEs LEADING TO DISCONTINUATION OF STUDY INTERVENTION**

AEs leading to discontinuation of study intervention are those events recorded as “Drug Withdrawal” for the question “Action Taken with study treatment” on the AE pages of the eCRF. A summary of AEs leading to discontinuation of study intervention by SOC and PT will be prepared.

A listing of all AEs leading to discontinuation of study intervention will be provided.

### **17.1.6. AEs LEADING TO DISCONTINUATION OF STUDY**

A summary of AEs leading to permanent discontinuation of study by SOC and PT will be prepared.

A listing of all AEs leading to permanent discontinuation of study will be provided.

### **17.1.7. COVID-19 RELATED AEs**

A summary of AEs related to COVID-19 by SOC and PT by cohort will be prepared, including exposure adjusted rates.

A listing of all AEs related to COVID-19 will be provided.

### **17.1.8. ADVERSE EVENTS OF SPECIAL INTEREST**

AESIs are events of scientific and medical interest specific to the further understanding of study intervention safety profile and require close monitoring and rapid communication by the investigators to the Sponsor. AESIs for AZD1222 are based on Brighton Collaboration case definitions (SPEAC 2020), clinical experience, and scientific interest. See [APPENDIX 7](#) for a listing and description of AZD1222 AESIs.

AESIs will be recorded from Day 1, post first study intervention, through the last participant’s contact. A summary of AESIs by categories and sub-categories listed in [APPENDIX 7](#) and PT and by cohort will be prepared, including exposure adjusted rates. The summary will also include the number and percentage of participants with any neurologic and/or neuroinflammatory AESIs. Should a participant experience multiple events within a category or PT, the participant will be counted only once for that category or PT. A summary of related AESIs by category and PT will also be prepared, including exposure adjusted rates. A summary of AESIs by severity grade (Grade 1, Grade 2 and Grade  $\geq 3$ ) and a summary of related AESIs by severity grade will be prepared.

A listing of all AESIs including those prior to the first vaccination will be provided.

#### **17.1.9. MEDICALLY ATTENDED ADVERSE EVENTS**

MAAEs are AEs leading to medically-attended visits that were not routine visits for physical examination or vaccination, such as an emergency room visit, or an otherwise unscheduled visit to or from medical personnel (medical doctor) for any reason. AEs, including abnormal vital signs, identified on a routine study visit or during the scheduled illness visits will not be considered MAAEs. MAAEs will be recorded from Day 1, post first study intervention, through the last participant's contact.

A summary of MAAEs by SOC and PT by cohort will be prepared, including exposure adjusted rates. Should a participant experience multiple events within a SOC or PT, the participant will be counted only once for that SOC or PT.

A listing of all MAAEs will be provided.

#### **17.1.10. VASCULAR DISORDERS OF EMBOLISM AND THROMBOSIS**

A summary of Vascular Disorders of Embolism and Thrombosis events by PT by cohort will be prepared, including exposure adjusted rates.

### **17.2. SOLICITED ADVERSE EVENTS**

Solicited AEs are local or systemic predefined AEs for reactogenicity assessment. Solicited AEs will be collected in a Solicited AE eDiary for 7 days following each dose of AZD1222. The set of solicited AEs associated with reactogenicity are presented below:

Local	Systemic
Pain at the site of injection	Fever ( $> 100^{\circ}\text{F}$ [ $> 37.8^{\circ}\text{C}$ ]) a
Erythema/redness at the site of injection b	Chills
Tenderness	Muscle pains
Induration/swelling at the site of injection b	Fatigue
	Headache
	Malaise
	Nausea
	Vomiting

aFever measured by any route. Investigators who consider a temperature lower than this cut-off as a fever or a 'fever' reported by participants

without documentation by a thermometer should record the event as 'elevated body temperature'.

bSwelling and redness must be  $\geq 0.6$  centimetres in diameter.

Severity will be assessed for solicited AEs by the participant according to toxicity grading scales modified and abridged from the FDA grading guidance (FDA, 2007). The measurements of the longest part of redness and swelling of injection sites will also be collected. These measurements will be used to derive severity grades based on the criteria presented in [APPENDIX 3](#). Severity grading for systemic solicited AE, i.e., fever are derived based on criteria presented in [APPENDIX 4](#). Because solicited AEs are expected to occur after vaccination, they will not be assessed for relationship to study intervention.

Solicited AEs for 7 days following each dose of study intervention will be summarized for each dose and overall. Each solicited AE will be summarized at the following time intervals: Days 1-8, and daily during the intervals Day 1 to Day 8. For each time interval, the count and percentage of participants will be determined for each of the following categories: participants evaluated, participants without any events, participants with any event, mild events, moderate events, severe events, and potentially life-threatening events. Participants should not be double counted; therefore, the event of greatest severity will be used for participants with more than 1 episode of the same event. Similar counts and percentages will be presented for solicited local AEs and solicited systemic AEs.

Quantitative and categorical summary of the day of first onset of each event and the number of days participants reported experiencing each event will be presented. The number of days a participant reported experiencing an event is calculated as the total of all days the participant reported the event, regardless of whether the symptom was reported on consecutive days (e.g., a headache reported on Day 1, Day 3, and Day 4 would be included with a duration of 3 days).

A listing of all solicited AEs will be provided.

### **17.3. DEATHS**

If any participants die during the study as recorded on the "Death Details" page of the eCRF, a listing of all deaths due to all causes will be provided.

### **17.4. LABORATORY EVALUATIONS**

For women participants of childbearing potential, a urine sample for pregnancy testing will be collected at screening and before each vaccination. Chemistry, hematology and coagulation tests will be performed as per the schedule of

events (refer to protocol, Section 1.3). A list of laboratory parameters to be included in the outputs is included in [APPENDIX 8](#).

Quantitative laboratory parameters reported as “< X”, i.e. below the lower limit of quantification (BLQ) or “> X”, i.e. above the upper limit of quantification (ULQ), will be converted to X for the purpose of quantitative summaries, but will be presented as recorded, i.e. as “< X” or “> X” in the listings.

The following summaries will be provided by cohort based on the SAF analysis set for each of chemistry, hematology and coagulation laboratory parameters:

- Observed and change from baseline in Standard International (SI) units by visit;
- Shift from baseline to the worst post-baseline observed value according to the FDA toxicity grades (for quantitative parameters with available FDA toxicity grades; refer to [Section 17.4.1](#))
- Listing of subjects with at least one laboratory observed value meeting a FDA toxicity grade  $\geq 3$  (for quantitative parameters with available FDA toxicity grades; refer to [Section 17.4.1](#))
- Shifts from baseline to the maximum/minimum post-baseline observed value according to normal range criteria (for quantitative parameters without FDA toxicity grades; refer to [Section 17.4.2](#));
- Listing of subjects with at least one abnormal laboratory observed value outside the normal range criteria (for quantitative parameters without FDA toxicity grades; refer to [Section 17.4.2](#));
- Maximum post-baseline ALT/AST observed value categorized as  $< 3 \times$  upper limit of normal (ULN),  $\geq 3$  to  $< 5 \times$  ULN,  $\geq 5$  to  $< 10 \times$  ULN or  $\geq 10$  ULN by maximum post-baseline total bilirubin observed value categorized as  $< 2 \times$  ULN or  $\geq 2 \times$  ULN;
- Scatter plots of the maximum post-baseline observed value in ALT value by the maximum post-baseline observed value in TBL value, both expressed as multiple of ULN;
- Scatter plots of the maximum post-baseline observed value in AST value by the maximum post-baseline observed value in TBL value, both expressed as multiple of ULN;
- A listing of subjects with at least one observed value in ALT value  $> 3 \times$  ULN, AST value  $> 3 \times$  ULN or TBL value  $\geq 2 \times$  ULN will be provided.

All laboratory data will be listed.

#### 17.4.1. FDA TOXICITY GRADES

Quantitative laboratory parameters with available FDA toxicity grades (FDA, 2007) will be categorized as follows where higher grades representing a more severe toxicity (refer to [APPENDIX 9](#) for each parameter toxicity grade criteria):

- Grade 1 (i.e., mild);
- Grade 2 (i.e., moderate);
- Grade 3 (i.e., severe)
- Grade 4 (i.e., potentially life-threatening)

Although not defined in the FDA toxicity grading system, 2007, non-missing laboratory parameter results not meeting any of the 4 grades defined in the FDA toxicity grading system will be categorized as 'No Event' for the purpose of the shift from baseline summaries.

